| Vital Signs, Pulse Oximetry ^C | | X | X | | X | X | X | X | X | X | X | X | X | X | X | X | X | X | X | X | X | X |
| ECG Triplicate Measurement | | X | X | | | | | | | | | | | X | | X | X | X | X | | X | |
| LABORATORY ASSESSMENTS | | | | | | | | | | | | | | | | | | | | | | |
| Serum Pregnancy Test ^d | | X | X | | | | | | | | | | | | | | | | | | | |
| Coagulation | | X | X | | | | | | | | | | X | X | X | X | | X | X | X | X | |
| Hematology, Chemistry | | X | X | | | | | | | | | | X | X | X | X | | X | X | X | X | |
| Blood Glucose Test | | X | X | | | | | | X | | | | X | X | X | X | | X | X | X | X | |
| Cytokine/CRP (Local lab) | | X | X | | | | | | X | | | | X | X | X | X | | X | X | X | X | |
| Urinalysis/Dipstick | | X | X | | | | | | | | | | | X | | X | | | | | X | |
| Hepatitis Serology, HIV, HLA | | X | | | | | | | | | | | | | | | | | | | | |
| ACTH, ANA, ANCA ^k | | | | | | | | | | | | | | | | X | | | | | | |

Footnotes defined on next page of the table

EOI = End of Infusion; EOT = End of Treatment; LTFU = Long Term Follow Up; SCR = Screening; SFUP = Safety Follow Up

^a Hospitalization at start of AMG 596 cycle 1 will be for a minimum of 8 days from the start of the AMG 596 infusion, whereby AMG 404 will be administered on [REDACTED], and for at least 24 hours following completion of the AMG 596 infusion. All subjects will be hospitalized for at least 72 hours after a dose step of AMG 596 at cycle 1 (if applicable).

Subjects should be monitored intensely in hospital or outpatient clinic for at least 4 hours after start of each AMG 404 infusion from cycle 1 [REDACTED] onwards.

^b Clinical evaluations will include physical exam, ECOG, and weight. Screening only: demographics, medical/surgical history, and height will also be obtained.

^c Vital Signs will be repeated at least every 4 hours during the first 24 hours of infusion and every 6 hours during the minimum hospitalization period in each cycle. Vital signs will also be assessed prior to subject's discharge from hospital in order to detect possible signs and symptoms of infusion reactions.

^d Serum pregnancy test will be performed for all females unless surgically sterile or ≥ 2 years postmenopausal.

^e Radiological Assessment by MRI for tumor staging by modified RANO will be performed at screening (within 14 days of enrollment). If available, data from a prior imaging evaluation (historical data will be dated within 6 months of enrollment) will be entered at screening. Scans will include T2-weighted, T2/FLAIR, T1-weighted pre- and post-contrast enhanced and DW (selected sites only) images of the brain. All other known sites of disease should also be recorded and assessed.

[REDACTED]

⁹ If a subject discontinues after C1 this visit assessments will be considered EOT assessments. After EOT, please perform SFUP assessments as in [Table 16](#).

[REDACTED]

Adverse events are to be collected for an eligible subject once the subject is enrolled in the study. A subject is considered enrolled after meeting all eligibility criteria and treatment and cohort have been assigned. Adverse events occurring during the screening period will be documented as medical history.

^j ACTH to be done every 8 weeks (prior to cycles 1, 3, etc). ANA and ANCA (cytoplasmic and perinuclear) to be done at screening and then if clinically indicated.

Approved

- ^a For combination therapy, hospitalization at start of AMG 596 cycle 2 and all subsequent cycles, and after dose step (if applicable) at cycle 2 and all subsequent cycles, will be for a minimum of 72 hours after start of AMG 596 until cycle 5. Hospitalization will be at minimum of 48 hours after start of AMG 596 from cycle 6 onwards (per investigator's discretion). Subjects should be monitored intensely in hospital or outpatient clinic for at least 4 hours after start of each AMG 404 infusion from cycle 1 [REDACTED] onwards
- ^b Clinical evaluations will include physical exam, ECOG, and weight. Screening only: demographics, medical/surgical history, and height will also be obtained.
- ^c Vital Signs will be repeated at least every 4 hours during the first 24 hours of infusion and every 6 hours during the minimum hospitalization period in each cycle. Vital signs will also be assessed prior to subject's discharge from hospital in order to detect possible signs and symptoms of infusion reactions.
- ^d Serum pregnancy test will be performed for all females unless surgically sterile or ≥ 2 years postmenopausal
- ^e Radiological Assessment by MRI for tumor staging by modified RANO will be performed at screening (within 14 days of enrollment). If available, data from a prior imaging evaluation (historical data will be dated within 6 months of enrollment) will be entered at screening. Scans will include T2-weighted, T2/FLAIR, T1-weighted pre- and post-contrast enhanced and DW (selected sites only) images of the brain. All other known sites of disease should also be recorded and assessed.
- [REDACTED]

- Safety Follow Up to be performed 30 days (+/- 7 days) after EOT.
- ⁱ Adverse events are to be collected for an eligible subject once the subject is enrolled in the study. A subject is considered enrolled after meeting all eligibility criteria and treatment and cohort have been assigned. Adverse events occurring during the screening period will be documented as medical history.
- ^j Medications associated with AEs or SAEs occurring between the SFUP visit and End of Study must also be collected.
- ^k ACTH to be done every 8 weeks (prior to cycles 1, 3, etc). ANA and ANCA (cytoplasmic and perinuclear) to be done at screening and then if clinically indicated.

Approved

7.2 General Study Procedures

A signed and dated IRB/IEC approved ICF must be obtained prior to performing any study-specific procedures. All screening procedures must be performed within 14 days of day 1, unless otherwise noted. Subjects who meet the inclusion and exclusion criteria will be eligible to be enrolled in the study.

A subject may be rescreened up to 3 additional times during the study at the discretion of the investigator.

During the study, every effort should be made to perform the study procedures as indicated on the Schedules of Assessments ([Section 7.1](#), [Table 6](#), [Table 7](#), [Table 8](#), [Table 9](#), [Table 10](#), [Table 11](#), [Table 12](#), [Table 13](#), [Table 14](#), [Table 15](#) and [Table 16](#)).

AMG 596 dose step can be introduced on [REDACTED] of a cycle, and assessments for the first week of the step dose ([REDACTED]) must follow assessments for [REDACTED] of a cycle except for the pregnancy test. In case of step dosing, AMG 404 will be administered [REDACTED] after the AMG 596 target dose is achieved in cycle 1.

AMG 404 will be given every [REDACTED]. ECG triplicate measurements will be performed during first AMG 404 infusion at predose, EOI, and 4 hours after end of infusion for cycle 1. In all subsequent AMG 404 dose, ECG triplicate measurements will only be collected at predose and EOI.

Subjects will be seen in the clinic for study evaluations. When electrocardiograms (ECGs), vital signs, blood sample collections, biomarker sample collections, and biopsy sample collections occur on the same visit, ECGs and vital signs should be performed before samples (blood, biopsy) are collected. Blood samples must not be taken/drawn from the catheter port used for AMG 596 or AMG 404 infusion. If a permanent central line with more than one lumen is used, blood draws can be done via the lumen that is not used for drug administration. The time of blood sample collection must be recorded with the exact time of collection in the subject's medical records and in the eCRF (do not use the time that the samples were frozen or any other time point). If blood samples will be collected on the same day that the infusion bag is being changed, the blood samples must be collected before the infusion bag is changed.

The study specific manuals provide additional details regarding the requirements for these procedures.

Approved

Acceptable deviation windows are as follows:

- After completion of cycle 1 (AMG 596 and AMG 404), +/- 1 day for all visits if logistically necessary
- ECGs, biomarker [REDACTED] vital signs (incl. pulse oximetry):
 - ± 15-minute window if collected within the first 24 hours (excluding the 24-hour sample) after the start of an infusion (or dose step, if applicable).
 - ± 2-hour window if collected between 24 hours and 3 days after the start of an infusion (or dose step, if applicable).
 - Assessments after day 3 should be performed on the indicated study day, but not at a certain hour of the day.
 - ± 1day window if collected at D8 or later, or at the EOI.
- PK blood draws in cycles 1 - 3:
 - within two hours prior to treatment start / dose step (if applicable)
 - ± 15-minute window for samples taken within the first 24 hours after start of infusion and within 24 hours after EOI. In case of a dose step, the ± 15-minute window also applies to the samples taken within the first 24 hours after dose step.

Local laboratories should be used for the following assessments: hematology, clinical chemistry including cytokines, coagulation, urinalysis, hepatitis serology, HIV, and serum pregnancy tests. Additional parameters can be explored locally and centrally for safety evaluations. The following collections will be shipped to a central laboratory for analysis: blood samples for determination of plasma concentrations of [REDACTED]

[REDACTED]. Refer to the laboratory manual for detailed collection, processing, and shipping procedures.

Approved

Table 17. List of Analytes

| Chemistry | Hematology | Coagulation | Urinalysis | Other |
|---|-------------------------------|-------------|--|--|
| Sodium | RBC | PT | Specific gravity | C-reactive protein (CRP) |
| Potassium | Hemoglobin | PTT | pH | IL-6 |
| Chloride | Hematocrit | INR | Blood | Serum Pregnancy |
| Bicarbonate (HCO ₃) or carbon dioxide | Mean corpuscular volume (MCV) | Fibrinogen | Protein | HLA typing |
| Total protein | Platelets | AT III | Glucose | Hepatitis B surface antigen |
| Albumin | White blood cell differential | | BilirubinMicroscopic exam** (performed at the discretion of the Investigator) | Hepatitis C antibody |
| Calcium | • Total neutrophils | | | HIV* |
| Calcium corrected | • Eosinophils | | | ACTH*** |
| Glucose | • Basophils | | | ANA*** |
| Blood urea nitrogen or Urea | • Lymphocytes | | | ANCA*** (cytoplasmic and perinuclear) |
| Creatinine | • Monocytes | | | |
| Estimated CrCl | | | | |
| GFR, MDRD calculation | | | | |
| Total creatine kinase | | | | |
| Total bilirubin (TBL) | | | | |
| Direct bilirubin | | | | |
| Alkaline phosphatase (ALP) | | | | |
| Alanine aminotransferase (ALT) | | | | |
| Aspartate aminotransferase (AST) | | | | |
| TSH*** | | | | |
| Free T4*** | | | | |

* Hepatitis B surface antigen, Hepatitis C antibody, PCR for Hepatitis C RNA (if Hepatitis C antibody is positive), and HIV assessments are recommended.

** WBC, RBC, Epithelial Cells, Bacteria, Casts, and Crystals

*** Only applicable for AMG 404 infusion

ACTH = Adrenocorticotrophic hormone; ANA = Antinuclear Antibodies; ANCA = Antineutrophil cytoplasmic antibodies;

A serum pregnancy test will be performed locally at each site on all female unless they are surgically sterile or ≥ 2 years postmenopausal. On visits where required, the serum pregnancy test must be performed prior to dosing with investigational product. If the pregnancy test is positive at day 1 of cycle 1, the subject should not be given investigational product.

Approved

Additional procedures deemed necessary as part of standard of care or as required by local laws and regulations may be performed at the Investigator's discretion. This may include measurement of urine output, if deemed appropriate by the Investigator.

7.2.1 Pre-Screening and Screening

The pre-screening evaluation is optional and serves to pre-determine EGFRvIII-positivity. Up to 500 subjects diagnosed with glioblastoma or malignant glioma may undergo the pre-screening evaluation. Pre-screening can start after written informed consent for pre-screening has been obtained and should be completed prior to signing consent for study participation.

[REDACTED]

[figure not shown]
[REDACTED] After

EGFRvIII-positivity has been reported and prior to signing consent for study participation, the subject may still receive one or more antitumor-treatments. During pre-screening, investigators may also provide the results of EGFRvIII positive testing from local testing for trial enrollment. If prescreening is used for enrollment, then plasma must be collected at screening or pre-dose for confirmation of mutation status when the plasma assay is ready. When the plasma test is ready, then patients will be enrolled using this plasma assay.

Subjects may also enter directly into the screening period without pre-screening.

[REDACTED]

Approved

Approved

The following assessments will be completed during Screening:

- Confirmation that the ICF for participation in the study has been signed
- Demographic data including sex, age, race, and ethnicity will be collected in order to study their possible association with subject safety

- Clinical evaluation
 - Physical examination as per standard of care. Physical examination findings should be recorded on the appropriate eCRF
 - Medical/surgical history (medical history data becoming available after the screening period will also have to be collected)
 - Including renal/urinary history (including urine output)
 - ECOG performance status
 - Height and weight
- Neurological Evaluation
- Vital signs (ie, blood pressure, heart rate, respiratory rate, temperature)
- Pulse oximetry
- ECG triplicate measurement
- Laboratory assessments: hematology, chemistry, coagulation, urinalysis, serum pregnancy test (females only), hepatitis serology, and HIV, cytokines/CRP, blood glucose test
- Biomarker assessments: [REDACTED]
- Note: Test results confirming EGFRvIII positivity expire with start of any antitumor therapy between re-screenings and need to be repeated in this case.
- Imaging assessment collected at screening visit
- Data from prior imaging evaluation (historical imaging) within 6 months of enrollment.
- Serious adverse event reporting
- Documentation of concomitant and rescue medications. All prior cancer treatment therapies will be collected, and other prior therapies that were being taken as of signature of the informed consent should be collected. For prior therapies, collect therapy name, indication, dose, unit, frequency, start date, and stop date.

7.2.2 Treatment

All subjects will be hospitalized for the following periods:

Cycle 1:

- For the first [REDACTED] of AMG 596 monotherapy (Arm 1)
- For the first [REDACTED] of AMG 596 in combination with AMG 404 (Arm 2), hence AMG 404 will be administered on [REDACTED]
- For at least 24 hours following completion of AMG 596 cycle 1 for both Arm 1 and Arm 2
- For additional 72 hours after AMG 596 step dose if necessary

Cycle 2 and all subsequent cycles:

- For at least the first 72 hours of AMG 596 infusion in both Arm 1 and Arm 2
- For additional 72 hours after AMG 596 step dose if necessary.

Hospitalization may be shortened to 48 hours from the 6th cycle onwards at the discretion of the investigator.

AMG 404 can be administered in an outpatient setting starting from cycle 1 [REDACTED] onwards. Subjects should be monitored intensely in hospital or outpatient clinic for at least 4 hours after start of each AMG 404 infusion from cycle 1 [REDACTED] onwards.

Restart of the infusion should be performed in the clinic/hospital under the supervision of the investigator or designee and the subject should be hospitalized for a minimum of 24 hours when the infusion interruption meets the following criteria:

- associated to an AE, or
- interruption > 24 hours due to a pump related issue.

[figure not shown]

Dosing with AMG 596 or AMG 596 in combination with AMG 404 can continue unless the subject becomes intolerant to investigational product, the signs and symptoms of clinical progression are evident as determined by the investigator, or the subject withdraws consent. Tumor evaluations by MRI will occur every 10 to 12 weeks from start of treatment. Earlier assessments can be made if clinically indicated at the discretion of the managing physician. Modified RANO criteria ([Appendix D](#)) will be used allowing subjects to stay on study until clinically significant disease progression if no other treatment discontinuation criteria apply. Upon discussion with the Sponsor, subjects may continue to receive treatment after radiographic confirmation of progressive disease as long as they continue to derive clinical benefit in the opinion of the investigator and until further increase in tumor burden. For analysis purposes, date of PD is the date of initial observed PD.

Investigational product is to be administered after all other protocol required pre-dose assessments have been performed on day 1 of each cycle.

The results from laboratory tests taken on day prior to infusion start do not have to be available before start of treatment with AMG 596. Laboratory assessments completed within 24 hours prior to treatment start do not have to be repeated on day 1 prior to infusion start.

The following procedures will be completed during the treatment period at the times designated in the Schedule of Assessments ([Section 7.1](#)). Treatment period starts when

[figure not shown]
the first cIV infusion of AMG 596 is administered to a subject. For a full list of study procedures, including the timing of each procedure, please refer to [Section 7](#) and the Schedule of Assessments.

- Hospitalization
- Clinical evaluation
 - Physical examination as per standard of care. Physical examination findings should be recorded on the appropriate eCRF.
 - ECOG performance status
 - Weight
- Neurological Evaluation
- Vital signs (ie, blood pressure, heart rate, respiratory rate, temperature)
- Pulse oximetry
- ECG triplicate measurement
- Laboratory assessments: hematology, chemistry, coagulation, urinalysis, serum pregnancy test (females only), blood glucose test, cytokines/CRP
- Biomarker assessments: 

- 
- Imaging Assessment
- Serious adverse event reporting
- Adverse event reporting
- Documentation of concomitant and rescue medications

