210. Treatment with non-topical systemic corticosteroids within 14 days before enrollment (day 1) (exemption: prophylactic treatment with dexamethasone as defined in [section 6.5](#), and systemic corticosteroid doses of ≤ 2 mg of dexamethasone (or equivalent) per day after consultation with Sponsor,)
211. Prior participation in an investigational study (drug, procedure or device) within 21 days of study day 1
212. Major surgery within 7 days of study day 1 with the exception of biopsy and long line insertion
213. History or evidence of any other clinically significant disorder, condition or disease that, in the opinion of the investigator or Amgen physician, if consulted, would pose a risk to subject safety or interfere with the study evaluation, procedures or completion
214. Male and female of reproductive potential who are unwilling to practice highly effective method(s) of birth control while on study and through 30 days after receiving the last dose of AMG 596 and through 4 months (120 days) after receiving the last dose of AMG 404.
 - Criteria for women of non-reproductive potential is as follows:
 - Postmenopausal as defined as:
 - Age of 55 years with cessation of menses for 12 months or more, OR
 - Age < 55 years and no spontaneous menses for at least 2 years, OR
 - Age < 55 years and spontaneous menses within the past year, but currently amenorrheic (eg, spontaneous or secondary to chemotherapy) AND with postmenopausal gonadotropin levels (luteinizing hormone and follicle-stimulating hormone level > 40 IU/L) or postmenopausal estradiol levels (< 5 ng/dL) according to the definition of “postmenopausal range” for the laboratory involved; OR
 - History of hysterectomy; OR
 - History of bilateral oophorectomy

Highly effective methods of birth control include sexual abstinence (male, female); vasectomy; bilateral tubal ligation/occlusion; hormonal birth control or intrauterine device (IUD) (female).

215. Female who is lactating/breastfeeding or who plans to breastfeed while on study through 30 days after receiving the last dose of AMG 596 and through 4 months (120 days) after receiving the last dose of AMG 404.
216. Female with a positive pregnancy test.
217. Female planning to become pregnant while on study through 30 days after receiving the last dose of AMG 596 and through 4 months (120 days) after receiving the last dose of AMG 404 infusion.

Approved

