The subject identification number must remain constant throughout the entire clinical study; it must not be changed after initial assignment, including if a subject is rescreened.

All screening tests and procedures should be performed within 14 days before enrollment, unless otherwise indicated. Screening may pause between shipment of tissue samples for EGFRvIII analysis and availability of test result and this time will be deducted from screening time if no other evaluations were done in this screening pause. Laboratory assessments used to determine subject eligibility may be repeated once for confirmation (up to a total of 2 times during the 14-day screening period) if necessary before the subject is considered a screen failure. If any assessments are repeated during the screening period, the value that is closest to the enrollment date will apply for the determination of eligibility and should be recorded in the screening eCRF.

Subjects who do not meet the eligibility criteria within the 14-day effective screening period will not be eligible for enrollment. Subjects may be re-screened up to 3 times at

the discretion of the investigator. The subject must be re-consented if a re-screening attempt occurs outside the 14-day screening period. Hepatitis serology and HIV test do not need to be repeated in case of re-screening if they were performed within 6 weeks prior to start of treatment with AMG 596. Test results confirming EGFRvIII-positivity expire with start of any antitumor therapy between re-screenings and need to be repeated in this case.

Subjects who are deemed ineligible will be documented as screen failures.

Subjects may be eligible to enroll once all screening tests and procedures are completed and results indicate that all eligibility criteria are met. A site representative will complete and send the enrollment eligibility worksheet to the sponsor or designee. The Amgen representative will acknowledge receipt and send confirmation of cohort and dose level assignment for the subject.

Screening assessments of new subjects can start upon DLT period completion and before the dose level review meeting (DLRM) of the preceding dose. Sites are allowed to start pre-screening subjects after the study site activation.

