7.3.13 Serum Pregnancy Test

[figure not shown]
A serum qualitative pregnancy test will be performed locally at each site on all females unless they are surgically sterile or ≥ 2 years postmenopausal. On visits where required, the serum pregnancy test must be performed prior to dosing with investigational product. If the pregnancy test is positive at day 1 of cycle 1, the subject should not be given investigational product. If the pregnancy test is positive at any other visit, then investigational product must be held, and a confirmatory quantitative serum pregnancy test must be done. If the confirmatory quantitative serum pregnancy test is positive, the investigational product (AMG 596) must be discontinued. If the quantitative pregnancy test is negative the subject should restart infusion per the criteria in [Section 6.2.4](#).

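### Section 7.2.2 lets AMG 596 start with day-before laboratory results pending and does not exempt the serum pregnancy test, so the text does not ensure that the no-product and hold rules act before exposure

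*Protocol*

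**What the plan says.** Section 7.2.2 of the protocol gives two permissions for laboratory work around the start of an infusion. Results of "laboratory tests taken on day prior to infusion start do not have to be available before start of treatment with AMG 596". Also, "Laboratory assessments completed within 24 hours prior to treatment start do not have to be repeated on day 1 prior to infusion start". The procedure list in the same section reads "Laboratory assessments: hematology, chemistry, coagulation, urinalysis, serum pregnancy test (females only), blood glucose test, cytokines/CRP", so the pregnancy test falls within the class that the permissions cover. No test is excepted.

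The pregnancy rules stand elsewhere. Section 7.2 says "On visits where required, the serum pregnancy test must be performed prior to dosing with investigational product". Section 7.3.13 says "If the pregnancy test is positive at day 1 of cycle 1, the subject should not be given investigational product" and, for later visits, "If the pregnancy test is positive at any other visit, then investigational product must be held". A quantitative test then follows: if it is positive, AMG 596 is discontinued; if it is negative, the infusion restarts under Section 6.2.4.

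At entry, exclusion 216 is "Female with a positive pregnancy test", and Section 5 says "Subjects may be eligible to enroll once all screening tests and procedures are completed and results indicate that all eligibility criteria are met".

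**The concern.** The no-product rule and the hold rule can prevent exposure only if someone has read the result before the pump starts. Section 7.2.2 lets the pump start before day-before results are back, and no section says that the pregnancy test is outside that permission or that 7.3.13 overrides it. A site could draw the sample on the day before, treat it as replacing the day 1 sample, start AMG 596, and learn of a positive result while the drug is running. It could reasonably believe it had complied throughout. What is at stake is avoidable exposure of a pregnant subject to an investigational T-cell engager.

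**Working it through.** The plan states no figure on this point, so the main check is to set the rules side by side.

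1. **Does the permission reach the pregnancy test?** Section 7.2.2 speaks of laboratory tests generally and lists the serum pregnancy test as one. Section 7.2 also groups it with the locally run laboratory tests. I found no exemption or order of precedence in 7.2, 7.2.2, 7.3.13, exclusion 216 or the legible schedule footnotes.

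2. **Do the pregnancy rules require a known result?** Sections 7.2 and 7.3.13 require the test to be performed before dosing. Section 7.2.2 likewise requires pre-dose assessments to have been performed before product is given on day 1 of each cycle. None of them says that the result must be available. The rules on positive results imply it but do not state it.

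3. **Cycle 1.** The screening test is a separate check, its result must satisfy eligibility, and Section 7.2 places screening within 14 days of day 1. Section 5 allows a screening pause for EGFRvIII testing, so the calendar interval can be longer. This protection is substantial but incomplete, because the pre-dose test exists to catch what screening missed or predated.

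4. **Cycle 2 onward.** Seven schedules apply: Tables 7, 9, 11, 12, 14, 15 and 16. The pregnancy row can be read in three of them (7, 11 and 15), and each shows the pre-dose test as the only check in those cycles. Table 15 also covers cycle 1, where it adds the screening test. The laboratory lists for end of treatment (7.2.3) and safety follow-up (7.2.4) omit the pregnancy test, and Section 7.2 excepts it from the assessments repeated at a dose step.

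5. **Age of the last known negative at the start of cycle 2**, taking the cycle 1 pre-dose test as that negative:
   - Formula: age = infusion length + break.
   - Infusion length: 28 days (Table 13 title). The break is redacted in the body. The Amendment 5 log, in text added to Section 6.2.1.1, gives 28 days on and 14 days off.
   - On that schedule: 28 + 14 = 42 days.
   - Section 6.2.1.1 allows breaks of more than 21 days after consultation with the sponsor. With such a break the age exceeds 28 + 21 = 49 days.

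6. **How far stopping limits exposure.** Section 2.5.3.1 predicts a half-life of 2.9 hours. Assuming first-order elimination, five half-lives are 5 × 2.9 = 14.5 hours, and the fraction cleared is 1 − 2⁻⁵ = 0.969, about 97%. This bounds the time on drug after stopping. It does not undo the exposure before stopping.

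**The case against.** The strongest reply is that ordinary reading settles the matter. Section 7.3.13 deals with this one test, while 7.2.2 is a general logistics sentence, so the specific rule should prevail. A rule that forbids dosing on a positive cycle 1 day 1 test makes sense only if the result is known. The word for finished assessments in the 24-hour sentence may mean resulted, in which case a pending test would have to be repeated on day 1. The permission covers only samples from the day before. For later visits, 7.3.13 prescribes hold, confirm and restart, which fits an infusion already running. Sections 6.2.5 and 8.3.1 also make pregnancy a ground for stopping treatment.

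Much of this stands. A reader might infer that 7.2.2 contradicts 7.2 and 7.3.13. The documents do not support that: 7.2.2 permits a pending result but does not require one, a day-before sample satisfies the timing rule as worded, and the later-visit procedure can be followed after a start. A reader might also infer that no schedule has any other pregnancy check from cycle 2. That cannot be said either, because the grids of Tables 9, 12, 14 and 16 are not in the available text.

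What remains is that the intended reading has to be inferred. Even if a pending test must be repeated on day 1, no sentence says that the repeat must be read before the start. Hold-and-restart limits an exposure but does not prevent one.

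**Conclusion.** The point holds as a minor safety-wording gap: the text does not ensure that a positive pregnancy result is known in time to prevent exposure. The gap is small at cycle 1 and matters most from cycle 2.

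The event should be rare. The test applies only to females who are neither surgically sterile nor at least 2 years postmenopausal, and exclusion 214 requires highly effective contraception. The documents give no count, and the 42-day figure is an interval between tests, not a risk. It assumes that the on/off schedule in the Amendment 5 log applies.

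Mitigation is real: from cycle 2, subjects are in hospital for at least the first 72 hours (48 hours possible from cycle 6), and AMG 596 is expected to clear quickly once stopped. The half-life behind that expectation is a prediction. The protocol itself asks for contraception until 30 days after the last AMG 596 dose and 120 days after the last AMG 404 dose.

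A reader might look for an effect on DLT attribution, response or sample size. Nothing in the documents points to one.

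**What to change.** Add to Section 7.2.2, after the two permissions: *This does not apply to the serum pregnancy test; a negative result (or a negative confirmatory quantitative test under 7.3.13) must be known before each AMG 596 infusion for which the test is scheduled.*

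All other laboratory tests keep the current permission, and the 24-hour sampling window stays. For later cycles this goes a little further than the present hold-and-confirm rule, so the sponsor should adopt it as a deliberate tightening. The test is already scheduled and run at local laboratories, so the cost is one sentence and an occasional start delayed by a few hours.
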